6.1.2 Secondary study parameters/endpoints

To determine if MSC treatment in (near-)term infants with PAIS is safe in the subacute setting, patients will be monitored until the age of 3 months. Subacute safety is defined primarily as the absence of treatment-related serious adverse events (SAEs) according to the Consolidated Standards of Reporting Trials (chapter 7.2) until the age of 3 months. Patients will then be asked to report on other SAEs, including infections, during the first three months of age. Whenever their child experiences fever, or other signs of infection/inflammation, there will be tested for bactermia, systemic infections and/or post-administration virus infections.

To determine if MSC treatment in (near-)term infants with PAIS is safe at 3 months in terms of cerebral tumorigenicity, infants will be scanned using MRI prior to MSC treatment and at 3 months of age. Long-term adverse effects on the brain in terms of tumorigenicity will be determined using this MRI, which is part of regular stroke follow-up program. Scans will be assessed by a pediatric radiologist to see if there are any adverse events on the brain (including tumor formation).

All MRI investigations will be performed on a 3.0 Tesla MR system. Infants will be sedated with a combination of chlorpromazine (0.5 mg/kg), pethidine (2 mg/kg), and promethazine (0.5 mg/kg) intramuscularly, which is part of our standard MRI procedure. During MR

examination the neonates will be placed in a vacuum fixation pillow (Med Vac Infant Immobilizer Bag, Radstadt, Austria) to prevent movement. Monitoring will be performed using pulse oximetry (Nonin, Minneapolis, MN) and respiration rate will be observed using the standard Philips equipment (Philips Medical Systems, Best, Netherlands). For hearing protection we will use: Minimuffs® (Natus Medical Incorporated, San Carlos, CA, USA), Earmuffs (EM's 4 Kids, Brisbane, Australia) and a passive acoustic noise dampener, the acoustic hood that properly fitted in the bore of the MRI scanner (Intera, Philips Medical, Best, Holland).

6.1.3 Other study parameters

None.

6.2 Randomisation, blinding and treatment allocation

Not applicable.

6.3 Study procedures

A description of all procedures, techniques and tests that are used to assess the defined study endpoints is given in chapters 6.1.1 and 6.1.2. A schedule including the timeline of all assessments is given in the flowchart of chapter 2.5. In summary, all procedures that subjects must undergo are:

- Intensive monitoring of vital signs at baseline until at least 24 hours after MSC treatment.
- Blood samples will be collected before and 24 hours after administration of MSCs. Blood samples are taken routinely in the hospital for clinical purposes, but some extra material (0.5-1 mL) will be collected to determine infection markers CRP, procalcitonin and complete blood count. These samples will be combined with routine blood sampling and taken from routinely placed (arterial) catheters.
- MRI investigation including 3D-T1, T2 weighted, DWI, DTI and MRspectoscropy sequences within 7 days after clinical presentation suggestive of PAIS
- Repeated MRI investigation including 3D-T1, T2 weighted, DWI, DTI and MR-spectroscopy sequences at 3 months of age.

These procedures are all part of clinical care for neonates with PAIS.

6.4 Withdrawal of individual subjects

Subjects can leave the study at any time for any reason if they wish to do so without any consequences. The investigator or physician can decide to withdraw a subject from the study for urgent medical reasons. Withdrawal from this study has no consequences for medical treatment of the patient.

6.4.1 Specific criteria for withdrawal

Not applicable.

6.5 Replacement of individual subjects after withdrawal

Not applicable.

6.6 Follow-up of subjects withdrawn from treatment

Not applicable.

6.7 Premature termination of the study

The study may be terminated prematurely for safety or futility reasons if there are AEs or SAEs as defined by chapter 7.

We will use the following stopping rules:

- If the region of infarction, as defined on T2 weighted MR imaging and/or DWI, increases by >20% after treatment with MSCs in 3 different patients.
- If there appear to be any adverse effects that might be related to admission of MSCs in 3 different patients. These adverse effects include:
 - Systemic infections / meningitis
 - o Hemorrhagic transformation of the infarction
 - Gastrointestinal hemorrhage
 - o Thromboembolism
 - Formation of malignancies
- Unexpected and unaccountable deterioration of clinical situation, for example persistent seizures, after treatment with MSCs in 3 different patients. Usually, stroke-related seizures will disappear within three days following their onset and treated with anti-epileptic drugs.
- Mortality after treatment with MSCs in one patient will stop the study temporarily until an investigation has been performed.

Continuation of the study will only take place after the first three infants completed their second MRI scan at 3 months of age. This will safeguard that all stopping criteria will be monitored closely and the study may be terminated prematurely in time when stopping criteria are met.

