7. SAFETY REPORTING

7.1 Section 10 WMO event

In accordance to section 10, subsection 4, of the WMO, the sponsor will suspend the study if there is sufficient ground that continuation of the study will jeopardise subject health or safety. The sponsor will notify the accredited METC without undue delay of a temporary halt including the reason for such an action. The study will be suspended pending a further positive decision by the accredited METC. The investigator will take care that all subjects are kept informed.

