7.5 Data Safety Monitoring Board (DSMB)

A DSMB will be established to perform ongoing safety surveillance and to perform interim analyses on the safety data. This committee will be an independent committee. The DSMB is composed of 4 members from the UMCU: three are members of the internal DSMB of the UMCU and one member has clinical expertise as paediatric neurologist. Each member has no conflict of interest with the study. The task and responsibility of the DSMB are described in the DSMB charter. CVs of each DSMB member are added to the DSMB charter.

The DSMB may decide to terminate the trial prematurely using the stopping criteria as stated in chapter 6.7 of this protocol.

The advice(s) of the DSMB will only be sent to the sponsor of the study. Should the sponsor decide not to fully implement the advice of the DSMB, the sponsor will send the advice to the reviewing METC, including a note to substantiate why (part of) the advice of the DSMB will not be followed.

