11.2 Synthesis

Adverse events, observed by the attending physician, which are expected or possibly related to the infusion of the product, are reported to the head of the CTF. Adverse events will be reported in a database, including patient characteristics and product characteristics. Adverse events will be evaluated with the Medical Director of the CTF in their weekly meetings. We will report the observed adverse events to the Dutch Health Inspectorate. Serious adverse events will be reported within 48 hours after the event has happened.

Planned pharmacovigilance actions for potential risks

1. Acute adverse effects: Administration Reaction, during and shortly after administration Planned actions:

 Monitoring of heart rate and blood pressure. And development of dyspnoea, nausea/vomiting, flushing, diarrhea, during or within 1 hour from the administration of the investigational product

- Monitoring temperature during or within 2 hours from the administration of the investigational product. During admission, temperature will be monitored very strictly, because hyperthermia after hypoxia-ischemia is associated with adverse (neurologic) outcome.(Laptook et al. 2008; Perlman 2006) If the temperature rises above 37.5°C we will use routinely clinical used precautions to prevent actual hyperthermia, such as lowering environmental temperature or use paracetamol.
- Development of exanthema or urticaria developing during or within 2 hours from the administration of the investigational product.

2. Subactue adverse effects:

Bacteremia due to bacterial contamination of product.

Planned actions: Monitoring of temperature during the following hours to days after intranasal administration. In case of contamination patients will be treated with antibiotics in case this is required.

Systemic infection due to use of MSC therapy

Planned actions: Close monitoring of first three patients by extra blood sampling and determination of infection markers. In case of systemic infection patients will be treated with appropriate antibiotics in case this is required, according to the antibiotics protocol used on the NICU.

• Post-administration virus infection.

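### Section 6.7 counts a non-fatal event traced to the product or donor, or an MSC-related anaphylactic shock, as only one of three patients; death is the only fixed one-case hold

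*Combined protocol and SAP*

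**What the plan says.** Section 6.7 (Premature termination of the study) opens with a permissive sentence: "The study may be terminated prematurely for safety or futility reasons if there are AEs or SAEs as defined by chapter 7". Its rules follow. The second reads "If there appear to be any adverse effects that might be related to admission of MSCs in 3 different patients" and gives an open list that includes systemic infection and malignancy. The last reads "Mortality after treatment with MSCs in one patient will stop the study temporarily until an investigation has been performed"; it does not require the death to be related to treatment. There is also one planned pause: "Continuation of the study will only take place after the first three infants completed their second MRI scan at 3 months of age".

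Other sections identify events with much stronger evidence of cause:

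- a virus infection for which the MSC donor is proven to be the source, which the protocol classes as an SAE (5.4, 11.1e, 11.2);
- bacteraemia from a contaminated product, defined as early fever together with a positive product culture (5.4, 11.1e);
- a malignancy with donor-derived tissue in or around it, found by genetic testing against the donor's HLA type (11.1e, 11.2);
- anaphylactic shock related to the administration, which is part of the definition of dose-limiting toxicity (1, 6.1.1, 8.1).

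For contamination, the planned action in 11.2 is "In case of contamination patients will be treated with antibiotics in case this is required". For the virus and malignancy cases it is a look-back, HLA-based testing, treatment of a malignancy, and classification of the event. None of these lines mentions holding further doses.

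Section 7.1 says "the sponsor will suspend the study if there is sufficient ground that continuation of the study will jeopardise subject health or safety", and then "The study will be suspended pending a further positive decision by the accredited METC". Section 7.5 says "The DSMB may decide to terminate the trial prematurely using the stopping criteria as stated in chapter 6.7 of this protocol".

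**The concern.** A three-patient threshold is reasonable for effects that stroke itself or intensive care could cause, since a one-case trigger there would produce false holds. It fits poorly where a test has traced the harm to the product or donor, or where a reaction has been judged related and the protocol itself calls it dose-limiting. Under rule 2 such a case waits for two more, and those two need only be possibly related.

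The protocol relies on its stopping rules, which it describes as tight, to limit unknown risks of a first intranasal use of these cells in humans, here in newborns (5.4, 9.4, 11.1e). Contamination or donor-borne infection may also reach another infant given cells from the same donor or batch. The documents do not say how many infants share one. Section 5.5.1 says only that the same MSCs are used in another trial at the centre. This is where a fixed temporary hold is easiest to justify, and 6.7 does not single it out.

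**Working it through.** The plan gives no operating characteristics for its stopping rules, so there is no figure to reproduce. The check is a comparison of the text plus simple timing arithmetic.

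**1. What follows from a single case**

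| First event in one infant | Fixed hold in 6.7? | Other stated consequence |
|---|---|---|
| Death, related or not | Yes, temporary | Expedited reporting (7.2.2) |
| Virus infection, donor proven as source | No, 1 of 3 | Look-back; SAE (11.2) |
| Early fever with positive product culture | No, 1 of 3 | Antibiotics if required (11.2) |
| Donor-derived malignancy | No, 1 of 3 | Genetic testing; SUSAR (11.1e) |
| Non-fatal MSC-related anaphylactic shock | No, 1 of 3 | Dose-limiting toxicity (1, 6.1.1, 8.1) |

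Rule 2's list is open and the rule covers any possibly related effect, so contamination bacteraemia, donor-borne virus infection and anaphylactic shock fall under it although they are not listed by name. The rule on unexplained clinical deterioration might also catch some of them, but it too needs three patients.

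**2. Against the protocol's own definition of safety.** Primary safety is the absence of treatment-related SAEs, followed by the absence of dose-limiting toxicity (6.1.1, 8.1). One donor-proven virus infection fails the first part, and one MSC-related anaphylactic shock fails the second. Rule 2 would still need two more patients.

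**3. Exposure under the fixed rules alone.** If the case is in infant 1 and is recognised at once, at most 3 − 1 = 2 more infants are dosed before the planned pause. If it is in infant 4, at least two more must be dosed before rule 2 can be met. All 10 − 4 = 6 remaining infants are dosed if fewer than two of them have a possibly related effect.

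**4. Time between infants.** Inputs: 10 infants (3.4) in 12 to 24 months (2.2), with 4.348 weeks per month.

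- Weeks per infant = months × 4.348 / 10. For 12 months this is 5.2 and for 24 months 10.4.
- If the pause of about 3 months falls inside that period: 9 × 4.348 / 10 = 3.9 and 21 × 4.348 / 10 = 9.1.
- Infants per week: 1/10.44 = 0.096 to 1/3.91 = 0.256.
- If infants arrive at random at a constant rate (assumption), P(gap ≤ 1 week) = 1 − exp(−rate), which is 0.09 to 0.23.

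The 48-hour SAE reporting and weekly review in 11.2 would therefore usually come before the next infant. The defect is mainly that the review has no stated consequence for dosing, and less that it comes late.

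**5. Where a hold helps.** Anaphylaxis, and infection or contamination recognised within days, can be acted on before the next dose. A malignancy sought on the 3-month MRI appears 3 × 4.348 = 13.0 weeks later. After the planned pause, on average 13.0/10.4 = 1.2 to 13.0/3.9 = 3.3 further infants would have been dosed by then, so a hold helps less.

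**The case against.** The strongest reply is section 7.1. It is mandatory once there is sufficient ground, and its restart condition, a positive ethics committee decision, is stricter than DSMB review. A donor proven to have transmitted a virus, with other infants still to be treated, would very likely meet that test. Other oversight adds to it: ongoing DSMB surveillance (7.5), an internal safety review committee (2.4), SAE and SUSAR reporting to the ethics committee (7.2.2, 7.2.3), and reporting to the head of the cell facility and the Health Inspectorate (11.2). All of this stands, and it limits the point to the absence of a fixed trigger. It does not remove the point: 7.1 does not say what counts as sufficient ground, the opening of 6.7 only permits termination, and 7.5 refers the DSMB back to criteria that contain no such one-case rule.

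A second reply is that donor or batch quarantine belongs in the IMPD, or DSMB procedure in its charter. Neither was available, so this is open.

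Two stronger readings are tempting. A reader might infer that dosing would continue until three traced cases had occurred. The documents do not support that: nothing in 6.7 tells the sponsor to wait, and 7.1 points the other way. A reader might also compare binomial probabilities. At an assumed 10% event rate, at least 3 of 10 has probability 0.070 and at least 1 of 10 has 1 − 0.9^10 = 0.651. This does not compare the two rules, because it gives traced events the same rate as all possibly related effects, of which they are a small subset. The protocol calls the contamination and viral risks minimal, and no rate for traced events is available.

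**Conclusion.** The point holds in a limited form. Rule 2 gives a first non-fatal event traced to product or donor, or a first non-fatal MSC-related anaphylactic shock, the same weight as an effect of doubtful cause. Suspension after one such case is probable through 7.1 and the existing oversight, but it depends on judgement; only death fixes it in advance. The evidence of cause is not equal across the four events. Donor-proven virus infection is the clearest, while the culture and donor-tissue findings are strong evidence short of full proof.

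The conclusion rests on the text and assumes no event rate. The timing figures assume the planned recruitment pace, and the one-week gap probabilities also assume random arrivals. Whether infants share a donor or batch, and whether the charter or IMPD already provides a hold, is unknown. This is a cheap improvement; the documents do not show that infants would be left unprotected.

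**What to change.** Add one line to 6.7, modelled on the mortality line. The sponsor or investigator stops dosing temporarily, without waiting for a DSMB judgement, after the first:

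- (a) virus infection with the MSC donor proven as source;
- (b) fever or infection meeting the protocol's own definition of contamination bacteraemia (early fever plus positive product culture);
- (c) malignancy or ectopic tissue with donor-derived cells;
- (d) anaphylactic shock related to MSC administration.

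Dosing resumes only after DSMB review, including whether other infants share the donor or batch, and after ethics committee agreement where 7.1 applies. Keep the three-patient rule for other possibly related effects. If the DSMB charter or IMPD already contains such a hold, cite it in 6.7 instead.

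The cost is one line here and a matching line in the charter. The board and the tests are already foreseen. The downside is a pause in which an eligible infant could miss the one-week treatment window (4.1): about 0.10 to 0.26 infants per week of hold. For an assumed four-week hold this is 4 × 0.096 = 0.38 to 4 × 0.256 = 1.02 infants.

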2.2 Duration

The duration of the study for each subject from inclusion until study end will be a maximum of 3 months, comprising a 1 week intervention period and follow-up until 3 months. Subject recruitment will be (approximately) 12-24 months, at the longest, depending on when the intended number of subjects is included. This study is expected to last for approximately 2.5 years, but will only end after all 10 subjects have been included, treated and have been seen for follow-up (MRI and neurodevelopmental testing) at 3 months of age.

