3.4 Sample size calculation

We aim to include 10 infants diagnosed with PAIS on MRI, who will be treated with MSCs via the nasal route.

Since this is a proof-of-principle study, the sample size is not only calculated based on expected power, but on the feasibility to be successful in recruitment of individuals needed for this study in order to complete the protocol in 2 years. It is expected that about 180,000 infants will be born alive per year.(StatLine 2015) Since the incidence of PAIS is 1/2300 there will be about 80 PAIS patients in the Netherlands yearly. A study from our group showed that about 26% of all PAIS patients involved the main MCA branch.(Harteman et al. 2012) Based

on this expectation, we think it will be feasible to recruit 10 PAIS patients in 12-24 months. We furthermore expect only a minimal drop out of initially included patients because PAIS is not life-threatening and follow-up is tightly regulated in all NICUs, including the WKZ.

Data analysis

Data will be analyzed on an intention to treat basis. SAEs are planned to be compared. Statistical analysis is described in detail in chapter 8.

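### Section 6.7 credits its single hold with timely stopping on every criterion, but for criteria read on the 3-month MRI the design does not ensure this after infant 3

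*Combined protocol and SAP*

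**What the plan says.** Section 6.7 lists the stopping rules. One is met if the infarct region on T2-weighted and/or diffusion-weighted MRI "increases by >20% after treatment with MSCs in 3 different patients". Another counts adverse effects possibly related to the cells, malignancy among them, and also needs three patients. There is one hold: the study goes beyond the first three infants only once they have had their second MRI. Section 6.7 then says this protects the monitoring of all criteria and that "the study may be terminated prematurely in time when stopping criteria are met".

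The scheduled study MRIs are one before treatment and one at 3 months (6.1.2, 6.3). Section 2.4 dates the second scan from treatment in one sentence and from birth in another; 6.1.2 and 6.7 date it from birth.

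On numbers and pace, 3.4 says "We aim to include 10 infants diagnosed with PAIS on MRI", and 2.2 says "Subject recruitment will be (approximately) 12-24 months, at the longest". Section 7.5 says "A DSMB will be established to perform ongoing safety surveillance" and gives the board interim analyses of safety data, with no timing. Section 8.3 says there is no interim analysis.

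**The concern.** The hold guarantees that scans 1-3 are available before infant 4 is dosed. From infant 4 on, nothing in the protocol ties dosing of one infant to the scan of an earlier one. Infarct growth can be judged only on a post-treatment MRI, and the only one scheduled is at 3 months. The growth rule also needs three affected infants, so the third may be scanned when few or no infants remain to be dosed.

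Sections 5.4, 9.4, 11.1e and 11.2 rely on the stopping rules of 6.7 to minimise or prevent risk in what the protocol describes as the first intranasal use of these cells in humans. If the claim in 6.7 is stronger than the design, the ethics committee and the DSMB weigh the risk against a safeguard that, for MRI findings, may act late.

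**Working it through.** **The plan's own figure.** Section 3.4 says "It is expected that about 180,000 infants will be born alive per year" and, at an incidence of 1/2300, "there will be about 80 PAIS patients in the Netherlands yearly". Check: 180,000/2300 = 78.3, in line with 80. With 26% involving the main MCA branch, 80 × 0.26 = 20.8 infants a year. Ten in 12 months needs 10/20.8 = 48% of them; ten in 24 months needs 5/20.8 = 24%. The sample size rests "on the feasibility to be successful in recruitment of individuals needed for this study". No operating characteristic is given for any stopping rule.

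**At the hold.** A three-patient rule can be met by then only if all three infants are affected, with probability p³: 0.8%, 2.7% and 12.5% at p = 20%, 30% and 50%.

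**After the hold.** Let g be the gap between doses (even spacing) and 3 months the time from dose to scan. The protocol does not say whether the hold is counted inside the recruitment period, so both readings are used:
- 12 months, hold inside: g = (12 − 3)/9 = 1.0 month
- 12 months, hold outside: g = 12/10 = 1.2 months
- 24 months: g = (24 − 3)/9 = 2.33 or 24/10 = 2.4 months

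Infants dosed within 3 months of a given infant: three at g = 1.0 (the third exactly at 3 months), two at g = 1.2, one at g = 2.33 or 2.4.

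The scan of infant k comes too late to spare anyone if (10 − k) × g ≤ 3. That is k ≥ 7 at g = 1.0, k ≥ 8 at g = 1.2 and k ≥ 9 at 24 months. The growth rule can therefore spare an infant only if the third affected infant is no later than m = 6, 7 or 8.

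**Probabilities.** With X(n) binomial(n, p), the rule is eventually met with probability P(X(10) ≥ 3), and in time with probability P(X(m) ≥ 3). The late share among trials that meet the rule is 1 − P(X(m) ≥ 3)/P(X(10) ≥ 3). The rate p is an assumption.

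| | p = 20% | p = 30% | p = 50% |
|---|---|---|---|
| Rule ever met, P(X(10) ≥ 3) | 0.322 | 0.617 | 0.945 |
| Late share, g = 1.0 (m = 6) | 69% | 59% | 31% |
| Late share, g = 1.2 (m = 7) | 54% | 43% | 18% |
| Late share, 24 months (m = 8) | 37% | 27% | 10% |
| Late, of all trials, 12 months | 17-22% | 26-36% | 17-29% |
| Late, of all trials, 24 months | 12% | 17% | 9% |

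Example at p = 30%, m = 6: P(X(6) ≥ 3) = 0.256, and 1 − 0.256/0.617 = 59%. Over p = 10%-60% the late share runs from 77% (p = 10%, g = 1.0) to 4% (p = 60%, 24 months).

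**Sensitivity.**
- Random arrivals (exponential gaps, 200,000 simulated trials per setting) give similar late shares. At p = 30% they are 57% (g = 1.0), 50% (g = 1.2) and 32% (24 months). At that rate, 7.9-8.8 infants are dosed on average when the rule is met, 0.9-1.8 of them after the infant who triggers it.
- Dating the scan from birth shortens the lag, taken here as about 2.5-2.75 months. The g = 1.2 and 24-month results do not change. The g = 1.0 case moves from m = 6 to m = 7 and so to the g = 1.2 row.

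**The case against.** A reader might infer that the safeguard fails for all seven infants after the hold, or that protection is mostly gone from then on. The documents do not support that. Scans of infants 4 to 6, 7 or 8 can still complete the rule before infant 10 is dosed. At 24 months the rule is met in time in 63%, 73% and 90% of the trials that meet it (p = 20%, 30%, 50%); at 12 months and p = 50%, in 69%-82%. Nor are many infants dosed in each lag: the number is 1-3, and only one at the slow pace.

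The late shares are conditional and rest on a growth rate that the documents do not give. The largest go with low rates, where the rule is seldom met at all: at p = 20% it is never met in 68% of trials. The protocol does not define timely termination; here it means before infant 10 is dosed.

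There are other routes to stopping. Section 6.7 allows termination for AEs or SAEs in general, a single death stops the study temporarily, and 7.1 obliges the sponsor to suspend on sufficient ground. Section 2.4 adds an internal safety review committee to the DSMB, and either could react to one or two abnormal scans. Infection and clinical deterioration show without MRI, and haemorrhage may show on cranial ultrasound before discharge. The DSMB charter, not available here, may already cover the handling of scans.

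All of this narrows the point and lowers its weight. It does not remove it: none of these bodies can use a scan that has not been made, and 6.7 makes its claim for every criterion.

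**Conclusion.** The point holds for infarct growth and for malignancy found on the 3-month MRI. For these, the single hold does not ensure timely termination once dosing resumes. The probabilities apply to the growth rule; malignancy shares the lag, but it sits in a list whose other effects may be seen sooner.

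The size depends on the assumed growth rate, the recruitment pace, whether the hold lies inside the 12 months, and how the MRI is dated. Late stopping is common at fast recruitment and rates of 10%-30% (43%-77% of trials that meet the rule). It is uncommon at slow recruitment and rates of 50%-60% (4%-10%). This is a correction of wording and reporting that is worth considering, not a defect that invalidates the design.

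**What to change.** - Reword the sentence in 6.7 so that it no longer claims timely termination for all criteria. State the lag of about 3 months between dose and scan, and that 1-3 further infants may be dosed within it at the planned pace.
- Have each scheduled 3-month MRI read against the 6.7 criteria as soon as it is done, and send the reading to the DSMB with a running tally of infants who meet a criterion, are scanned and clear, or are dosed but not yet scanned. If the DSMB charter already provides this, a cross-reference is enough.
- Reconcile the dating of the second MRI from treatment (2.4) with its dating from birth (2.4, 6.1.2, 6.7), and the absence of interim analysis in 8.3 with the DSMB interim analyses in 7.5.

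No new hold or stopping rule is proposed; whether a further pause is wanted is for the sponsor and the DSMB. The cost is wording in the protocol and possibly the charter, with no extra scans. The downside is a less favourable statement of the safeguard.
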